- 4.A.12 Patients must have absolute neutrophil count (segmented neutrophils and bands) 1,500 /μL and platelets > 100,000/μL within 28 days prior to Cycle 1, Day 1 unless decreased counts have been shown to be due to marrow involvement with NHL.

NOTE: For progression to treatment with Zevalin: Patients must have < 25% bone marrow involvement with lymphoma as determined after cycle 2 of ESHAP. For patients without bone marrow involvement, there must be adequate bone marrow reserves as defined under EXCLUSION. (These criteria must be strictly met for adequate patient safety.)

Additionally, patients must have:

- serum creatinine value < 2.0 and total bilirubin < 2.0.
- Platelet counts $\geq 150,000/\text{mm}^3$, these patients will receive a dose of 0.4 mCi/kg of Zevalin
- Platelet counts from 100,000/mm³ to 149,000/mm³, these patients will receive a 0.3 mCi/kg dose of Zevalin
- 4.A.13 Patients with renal insufficiency or renal failure (serum creatinine > 2.0 mg/dL; creatinine clearance < 50 ml/min) are not eligible for this study. A serum creatinine or creatinine clearance must be obtained within 28 days prior to Cycle 1, Day 1.
- 4.A.14 Pregnant or nursing women may not participate. Women or men of reproductive potential must agree to use an effective contraceptive method as determined by the treating physician from the time of Cycle 1, Day 1 to 6 months after receiving the Zevalin.
- 4.A.15 No prior malignancy is allowed except for adequately treated basal cell or squamous cell skin cancer, in situ cervical cancer, or other cancer for which the patient has been disease-free for 5 years.
- 4.A.16 If Day 28 falls on a weekend or holiday, the limit may be extended to the next working day. In calculating days of tests and measurements, the day a test or measurement is done is considered Day 0. Therefore, if a test is done on a Monday, the Monday 4 weeks later would be considered Day 28. This allows for efficient patient scheduling without exceeding the guidelines.
- 4.A.17 All patients must be informed of the investigational nature of this study and give written informed consent in accordance with institutional and federal guidelines.
- 4.A.18 Expected survival \geq 3 months

4.B Exclusion Criteria

- 4.B.1 Patients with impaired bone marrow reserve, as indicated by one or more of the following:
 - Platelet count < 100,000 cells/mm³
 - Hypocellular bone marrow (cellularity < 10%)

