 - Marked (>_10%) reduction in bone marrow precursors of one or more cell lines (granulocytic, megakaryocytic, erythroid) (beyond that which would be expected for the patient's age and bone marrow cellularity
 - History of failed stem cell collection
- 4.B.2 Prior radioimmunotherapy

- 4.B.3 Presence of CNS lymphoma. Patients must not have clinical evidence of central nervous system (CNS) involvement by lymphoma.
- 4.B.4 Patients with abnormal liver function: total bilirubin > 2.0 mg/dL
- 4.B.5 Patients with abnormal renal function: serum creatinine > 2.0 mg/dL or creatinine clearance < 50 ml/min.
- 4.B.6 Patients who have received prior external beam radiation therapy to > 25% of active bone marrow (involved field or regional)
- 4.B.7 Patients who have received G-CSF or GM-CSF therapy within 2 weeks prior to treatment
- 4.B.8 Serious nonmalignant disease or infection which, in the opinion of the investigator and/or the sponsor, would compromise other protocol objectives
- 4.B.9 Major surgery, other than diagnostic surgery, within 4 weeks
- 4.B.10 Patients with pleural effusion

4.C Number of Patients to be Enrolled

All patients who receive at least one dose of chemotherapy ESHAP will be considered evaluable and will be included in the analysis. Fifty-two evaluable patients are needed. Although it is considered highly unlikely that a patient who has given consent (enrolled) for treatment would not be treated, if this were to occur, an additional patient would be enrolled to meet the goal of 52 evaluable patients.

4.D Patient Enrollment Procedure

All ethical, regulatory, technical, and scientific approvals must be in place before study registrations will be accepted. All patients will be registered centrally with the Clinical Research Coordinator based in the Arizona Cancer Center at [contact]. The Clinical Research Coordinator will assign each patient a sequential number. Prior to registration, the fully signed informed consent must be presented and all inclusion and exclusion criteria will be reviewed with the registering investigator or designee. All source documentation needed to confirm eligibility must be available for this review.

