The above mentioned tests and assessment are to be performed within 28 days of Rituximab & Zevalin administration.

d. Rituxaimab Infusion (250 mg/m²) & ¹¹¹In Zevalin (Ibritumomab Tiuxetan Indium) infusion. (Please refer to section 7.B for detailed treatment administration)

5.C.2 Days 2, 3, 4 and 5

a. Gamma Scan: A scan is to be performed at 48-72 hours after ¹¹¹In Zevalin (Ibritumomab Tiuxetan Indium) infusion. Another optional scan may be performed at 90-120 hours after ¹¹¹In Zevalin (Ibritumomab Tiuxetan Indium) infusion.

CAUTION WILL BE TAKEN IN THE HANDLING OF ALL RADIOACTIVE SAMPLES ACCORDING TO STANDARD PROCEDURES AND PRACTICES AT THE CLINICAL SITE

The purpose of ¹¹¹In Zevalin (Ibritumomab Tiuxetan Indium) imaging is twofold:

- To evaluate biodistribution of whole body gamma camera images
- To assess whether biodistribution is acceptable to proceed with ⁹⁰Y Zevalin (Ibritumomab Tiuxetan Ytrium-90) radioimmunotherapy.

The biodistribution of ¹¹¹In Zevalin (Ibritumomab Tiuxetan Indium) should be assessed by a visual evaluation of whole body planar view anterior and posterior gamma images. A set of images at 48-72 hours after injection is required. To resolve ambiguities, optional images at other time points may be necessary. Images should be acquired using a large field of view gamma camera quipped with a medium energy collimator. Whole body anterior/posterior planar images should be acquired using a large field-of-view gamma camera and medium energy collimators. Suggested gamma camera settings: 256 x 1024 matrix; dual energy photopeaks set at 172 and 247 keV; 15% symmetric window; scan speed of 10 cm/min for the 48-72 hour scan, and 7-10 cm/min for subsequent scans.

> Expected biodistribution:

- Activity in the blood pool areas (heart, abdomen, neck, and extremities) may be faintly visible.
- Moderately high to high uptake in normal liver and spleen.
- Moderately low or very low uptake in normal kidneys, urinary bladder, and normal (uninvolved) bowel.
- Non-fixed areas within the bowel lumen that change position with time; delayed imaging as described above may be necessary to confirm gastrointestinal clearance.

Tumor uptake may be visualized in soft tissue as areas of increased intensity, and tumor-bearing areas in normal organs may be seen as areas of increased or decreased intensity. Tumor visualization on the ¹¹¹In Zevalin (Ibritumomab Tiuxetan Indium) scan is not required for ⁹⁰Y Zevalin (Ibritumomab Tiuxetan Ytrium-90) therapy.

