The radiolabeling kits should be stored in a secure refrigerator at 2 - 8°C. Zevalin solutions are stable at 2 - 8°C for up to 8 hours for ⁹⁰Y Zevalin and up to 12 hours for ¹¹¹In Zevalin following their preparation. Due to the relatively short half life of the ⁹⁰Y isotope, if not used soon after calibration time, the actual dose will have decayed and will require recalculation. For proper Rituxan storage instructions see the package insert in the appropriate Appendix.

6.C.5 111In Zevalin and 90Y Zevalin Treatment Protocol

The ¹¹¹In and ⁹⁰Y isotope order form must be completed and faxed to the designated isotope vendor preceding the initial Rituxan infusion. Patients will receive an initial infusion of 250 mg/m² Rituxan. (111 In Zevalin, 90-Y-Zevalin, and Rituximab will not be provided by Biogen Idec

Incorporated). Immediately following, patients will receive a fixed dose of 5.0 mCi of ¹¹¹In Zevalin. If the biodistribution is altered such that the safety risk would be unacceptable, the patient will be taken off study and not proceed with ⁹⁰Y Zevalin radioimmunotherapy. On Day 7, 8 or 9, patients must receive a second infusion of 250 mg/m² of Rituxan and either 0.4 mCi/kg or 0.3 mCi/kg of Zevalin based on most recent platelet counts. The exact dose of Zevalin will be based on the patient's weight during the most recent evaluation according to Table 4. **The maximum dose is not to exceed 32 mCi of ⁹⁰Y.**

Table 4. Dosing of Zevalin

Platelet Counts ≥ 150,000/mm ³	Platelet Counts 100,000/mm ³ to 149,000/mm ³
0.4 mCi ⁹⁰ Y/kg	0.3 mCi ⁹⁰ Y/kg
Dose will be calculated using actual body weight	Dose will be calculated using actual body weight
Not to exceed 32 mCi (Maximum Dose)	Not to exceed 32 mCi (Maximum Dose)

6.C.6 Zevalin Adverse Events

For an extensive review of adverse events refer to the Investigational Brochure. Safety data, except where indicated, are based upon 349 patients treated in 5 clinical studies with ZEVALIN. In all cases, the ZEVALIN regimen included two doses of RITUXAN. See the RITUXAN package insert for specific adverse event (AE) information for that product.

Table 5 lists most common nonhematologic adverse events in \geq 5% of patients. The table does not include hematologic AEs of neutropenia, thrombocytopenia, and anemia (See Table 6, Hematologic Toxicity).

 $Table \ 5$ Incidence of Nonhematologic† Adverse Events in ≥ 5 % of Patients in Clinical Trials with ZEVALIN Regimen During the Treatment Period*(N = 349)

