7 TREATMENT PLAN

All patients who qualify for this study will receive chemotherapy with ESHAP followed by treatment with Zevalin

7.A ESHAP REGIMEN DOSING

ESHAP chemotherapy: Patients will receive 2 cycles of cytoreductive chemotherapy according to the schedule described below. (Table 7)

TABLE 7 ESHAP CHEMOTHERAPY PLUS ZEVALIN

DRUG	DOSE	ROUTE	DAYS	INTERVAL
Etoposide	$40 \text{ mg/m}^{2/} \text{day}$	IV infusion over 1 hour	1,2,3,4	q 28 days for 2 cycles
Methylprednisolone	250 mg/day	IV push	1,2,3,4	q 28 days for 2 cycles
		_		
Cytarabine	2000 mg/m^2	IV infusion over 2 hours	4	q 28 days for 2 cycles
Cisplatin	25 mg/m ² /day	IV infusion at 1mg/min	1,2,3,4	q 28 days for 2 cycles

- The cycle length will be 28 days if bone marrow recovery allows. If recovery requires an additional week, then the second cycle will be postponed for a week.
- Either pegfilgastrim or filgastrim may be given at the investigator's discretion.

7.B RITUXIMAB, 111 IN ZEVALIN, AND 90 Y ZEVALIN ADMINISTRATION

The rituximab + ibritumomab tiuxetan regimen is given 4-6 weeks after completion of the second cycle of ESHAP. Treatment can be completed within 7 - 9 days in an outpatient setting

TABLE 8
Rituximab, 111In Zevalin, AND 90Y Zevalin Administration

AGENT	DOSE	ROUTE	DAYS	NOTES
Rituximab	250 mg/m ²	Slow IV	1, then 7, 8 or 9	Give prior to 111 In Zevalin
¹¹¹ In Zevalin	5 mCi	Slow IV push over 10 minutes	1	Give within 4 hours after rituximab
⁹⁰ Y Zevalin	Depends on platelet count (see Section 7.B.3)	Slow IV push over 10 minutes	7, 8, or 9	Give within 4 hours after rituximab

7.B.1 Rituxan & 111 In Zevalin Administration

1.6 mg of ¹¹¹In Zevalin (5.0 mCi of ¹¹¹In) will be used for radioimaging. The imaging dose of ¹¹¹In Zevalin will be administered by a 10-minute slow IV push injection immediately following the infusion of Rituxan. ¹¹¹In Zevalin may be directly injected by stopping the flow from the IV bag and injecting the radiolabeled antibody directly into the line. A 0.22 micron filter must be on line between the patient and the infusion port. Flush the line with at least 10 mL of normal saline after ¹¹¹In Zevalin has been injected. (See Appendix H).

a. Oral premedication (2 tablets [325 mg] of acetaminophen and 50 - 100 mg oral diphenhydramine hydrochloride) may be administered 30 - 60 minutes prior to starting each infusion of rituximab.

7.B.2 Radioimaging Schedule

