APPENDIX A

STUDY CALENDAR

4/1/2010

STUDY CALENDAR Page 1

					Ibritumomab Tiuxetan (Zevalin)			
Required Studies	Baseline	ESH	AP Treatm	ent		Regin	nen [∞]	
Visits (weeks or days)	Within28 days prior to C1, D1	Cycle 1 Day 1	Cycle 2 Day1	Cycle 2 Day 29	Day 1	Day 2,3,4,5	Day 7, 8, or 9	Day 35
PHYSICAL								
History / Physical / vital signs ^α	X		X	X	ΧП			
Height / Weight / BSA / PS	X		X	X	ΧП			
Disease Assessment	X			X				
Toxicity Assessment	X		X	X	ΧП			
LABORATORY								
CBC / differential / platelets	X		X	X	ΧП			\mathbf{X}^{Σ}
Serum Creatinine / BUN	X		X	X	ΧП			
AST/ ALT/ Alk. Phos/ T. Bilirubin^	X							
LDH	X							
BHCG [†]	X							
Beta 2- microglobulin	X							
Hepatitis B screen*	X							
Pathology Review [£]	X							
Bone marrow cytogenetics [¥]	X			X				
Bone marrow aspiration and Bx	X			X				
SCANS								
CT or PET Chest	X			X				
CT or PET Abdomen	X			X				
CT or PET Pelvis	X			X				
Gamma Scan						X≠		
TREATMENT								
ESHAP		X	X					
Rituximab 250 mg/m2					X		X	
Ibritumomab Tiuxetan Indium (¹¹¹ In Zevalin)					X			
Ibritumomab Tiuxetan Ytrium-90 (90Y Zevalin)							X	

- α Vital Signs consist of BP, temperature and pulse
- t Baseline for women of childbearing potential
- ¥ A scan is performed at 48-72 hours after 111In Zevalin. Another optional scan may be performed at 90-120 hours after 111In Zevalin.
- ∞ ¹¹¹In Zevalin is administered 4-6 weeks after completion of ESHAP.
- ٨ Required at Baseline and Encouraged to repeat as clinically indicated by Good Medical Practice.
- Encouraged by Good Medical Practice, but not required.
- ¥ Bone Marrow cytogenetics can be done at either Baseline or C2,D29, but must be done at least once.
- £ Pathology Review consists of a basic review of a pathology report. If possible submit: Representative H&E stained slides from the diagnostic biopsy, one representative paraffin block and one copy of the pathology report.
- Σ Starting Day 35 (+/- 7 days) a CBC w/ Diff and Platelet count should be done every week until nadir.
- Within 28 days prior to Rituximab & Zevalin administration..

STUDY CALENDAR Page 2

Required Studies	Restaging	Short-Term Follow-Up				Long-Term Follow-Up	Off-Study [#]
Visits (weeks or days)	3 mos post ⁹⁰ Y Zevalin	6 mos post Zevalin	12 mos post Zevalin	18 mos post Zevalin	24 mos post Zevalin	Follow-Up: Annually for 3 years [£]	Disease Progression or Removed from Study (within 4 weeks)
PHYSICAL							
History / physical / vital signs ^α	X	X	X	X	X	X	X

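### The written conditions for 90Y Zevalin set no explicit neutrophil minimum after ESHAP, and restate the marrow-reserve criteria only for patients without marrow involvement

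*Combined protocol and SAP*

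**What the plan says.** For study entry, 4.A.12 asks for an ANC of 1,500/µL and platelets above 100,000/µL within 28 days before Cycle 1 Day 1, "unless decreased counts have been shown to be due to marrow involvement with NHL".

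The NOTE under 4.A.12 then gives the conditions for proceeding to Zevalin and says they must be followed strictly for safety. They are:

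- marrow involvement below 25% after the second ESHAP cycle;
- on reserve, "For patients without bone marrow involvement, there must be adequate bone marrow reserves as defined under EXCLUSION";
- creatinine and bilirubin below 2.0;
- platelets of at least 100,000/mm³, with the dose set by the count.

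The reserve definition is in 4.B.1 and has four items: platelets below 100,000, cellularity below 10%, marked reduction of marrow precursors, and a past failed stem cell collection. None concerns neutrophils.

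On dosing, 6.C.5 prescribes "either 0.4 mCi/kg or 0.3 mCi/kg of Zevalin based on most recent platelet counts". Table 4, 7.B.3b and Appendix H repeat the platelet bands, and 7.B.3b forbids 90Y below 100,000. On timing, 7.B states: "The rituximab + ibritumomab tiuxetan regimen is given 4-6 weeks after completion of the second cycle of ESHAP". For the CBC with differential before the regimen, 5.C.1 says: "The above mentioned tests and assessment are to be performed within 28 days of Rituximab & Zevalin administration". The calendar footnote in Appendix A reads "Within 28 days prior to Rituximab & Zevalin administration", and the Day 7, 8 or 9 column schedules no CBC.

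**The concern.** Hematologic toxicity is the dose-limiting toxicity of 90Y Zevalin (6.C.6). Table 6 reports Grade 4 ANC toxicity in 30% of patients at 0.4 mCi/kg and 35% at 0.3 mCi/kg, with median ANC nadirs of 800 and 600 cells/mm³. Here 90Y follows two cycles of myelosuppressive chemotherapy, and Table 2 describes no Zevalin trial with such a lead-in.

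A patient could therefore meet every written condition and receive 90Y with an ANC below 1,500/µL. The marrow-reserve wording has a similar gap. The percentage of marrow occupied by lymphoma does not measure how much normal hematopoiesis remains. Yet the explicit post-ESHAP reserve check is written only for patients whose marrow is clear.

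**Working it through.** The plan gives no figure to reproduce. The check sets the rules side by side.

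| Rule | Applies to | Platelets | ANC | Cellularity and precursors |
|---|---|---|---|---|
| 4.A.12 and 4.B.1 at entry | All, before ESHAP | Yes | 1,500/µL, waived if low counts are due to marrow lymphoma | Yes |
| 8.A.1 | Next ESHAP cycle | Above 100,000 | Above 1,500, with a tumor exemption and a reduced-dose route after 2 weeks | No |
| 4.A.12 NOTE, marrow clear | Before Zevalin | At least 100,000 | None | Yes, through 4.B.1 |
| 4.A.12 NOTE, involvement >0% and <25% | Before Zevalin | At least 100,000 | None | Not stated |
| Table 4, 7.B.3b, Appendix H | 90Y dose | Bands; 7.B.3b sets a 100,000 floor | None | Not stated |

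1. Reserve items not explicitly re-checked in an involved marrow. 4.B.1 lists 4 items. The platelet item is required of everyone by the NOTE and 7.B.3b, and failed stem cell collection is a history item screened at entry. So 4 − 1 − 1 = 2 remain: cellularity and precursor reduction.

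2. Explicit neutrophil minimum for 90Y. There is none in the NOTE, Table 4, 7.B.3b or Appendix H. Nor do 3.A, 5.C or 8.C supply one. The 500/µL figure in 7.B.3d governs growth-factor use and is not a condition for dosing.

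3. Indirect holds.
   - 8.B.3, under rituximab post-infusion observation, stops treatment for a Grade 3 toxicity that lasts to the next infusion. Table 8 places 90Y within 4 hours after rituximab, so such a hold could also stop 90Y. The Table 6 footnote puts Grade 3 or 4 at ANC below 1,000. Read generously, 8.B.3 covers that range and leaves 1,000–1,499 uncovered. It names no count and needs a current one.
   - 13.B requires a second registration before Zevalin to check eligibility and dose, but lists no criteria. The ANC criterion is dated to Cycle 1 Day 1, so 13.B cannot supply a post-ESHAP value.
   - 11.A leaves withdrawal to the investigator's judgment, without a threshold.

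4. Effect on the primary endpoint of withholding 90Y. Under 4.C such a patient stays among the 52 evaluable. Each one who progresses within a year as a result moves observed 1-year PFS by 1/52 = 0.0192, or 1.9 percentage points.

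5. Age of the count under the fix. A CBC within 7 days before Zevalin Day 1 is 0 to 7 days old on that day. 90Y on Day 7, 8 or 9 comes 6 to 8 days later, so the CBC is 0 + 6 = 6 to 7 + 8 = 15 days old at 90Y.

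**The case against.** The best defense is that selection by platelets and marrow percentage is a reasoned choice. The dosimetry summary in 1.D.2 reports that these criteria screened patients effectively for safe treatment. That stands as support for those two criteria. It does not show that ANC can be left out. The two trials whose ANC rule is quoted, 106-03 and 106-04, also required about 1,500/mm³, and the summary limits its conclusion to the population studied.

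Timing also helps the plan. Zevalin starts at least 4 weeks after ESHAP. Section 6.A puts white-cell recovery after high-dose cisplatin at about three weeks and maximal etoposide myelotoxicity at 12–16 days. In SWOG 9911, radioimmunotherapy 4–8 weeks after six CHOP cycles was well tolerated. The agents and schedules differ, but this suggests that most patients will have recovered. It limits the likely number affected without supplying a rule for the rest.

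On reserve, 4.B.1 is worded as an unconditional exclusion, and 13.B can reasonably be read as re-applying it to everyone. That reading stands as a possibility, so this half is a clarification. Applying the 10% precursor criterion literally could also conflict with the allowance of up to 25% involvement in 3.A, and the fix must avoid that.

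Growth factor use (7.B.3d) and weekly CBCs from Day 35 (5.C.4) manage cytopenia; they are not conditions for giving 90Y.

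A reader might infer that nothing would stop 90Y in a severely neutropenic patient. The documents do not support that: 8.B.3 and investigator judgment remain. A reader might also infer that counts well over 28 days old are permitted at 90Y. That depends on how the start of the 4–6 week interval is read, and on counting the CBC window only to Zevalin Day 1. The calendar footnote can equally be counted to 90Y itself.

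**Conclusion.** The point holds as a gap in the written safety rules. No section states a neutrophil minimum for 90Y after ESHAP. Two of the four reserve items are not explicitly re-checked when residual involvement is above 0% and below 25%. The neutrophil half is the firmer one; the reserve half depends on how 13.B is read.

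The number of patients affected cannot be estimated. The documents give no rate of ANC below 1,500, low cellularity or precursor reduction after ESHAP. A reader might infer that involved patients are deliberately exempt from reserve criteria, or that harm at ANC 1,000–1,499 is established. The documents show neither: 4.B.1 applies to everyone at entry, and no outcome data are given for that range.

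The 1,500/µL value is taken from the entry criterion and the two earlier Zevalin trials; the documents do not derive it for patients after ESHAP. The change is a cheap improvement to patient safety and leaves the sample size and the test unchanged.

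**What to change.** 1. In the 4.A.12 NOTE and 7.B.3b, add ANC of at least 1,500/µL, with no exemption for marrow lymphoma. Apply it to the CBC with differential that sets the platelet-based 90Y dose, taken within 7 days before Zevalin Day 1. If the ANC is lower, repeat the CBC weekly and delay within the existing 4–6 week window. A patient who does not recover in that window does not receive 90Y, is followed as in 3.A, and stays evaluable under 4.C.

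2. In the NOTE and 13.B, state that the 4.B.1 reserve criteria are re-checked on the Cycle 2 Day 29 marrow for all patients. Precursor reduction is to be judged beyond what residual involvement below 25% itself explains, so that the 3.A allowance is kept.

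Cost: the marrow sample is already taken in everyone. The change adds at most about one CBC per patient, plus weekly repeats for those delayed: about 6 − 4 = 2 for a patient first checked at week 4. Some patients may be delayed or not receive 90Y, with the PFS effect per patient shown in the working. A limit remains: a count supported by growth factor could meet the threshold without showing reserve.
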